### **6.2 Participant Exclusion Criteria**

- absolute neutrophil count (ANC) of <500/ $\mu$ l, platelet count of <20,000/ $\mu$ l or INR >2.0
- acupuncture within two weeks prior to HiChemo (to avoid residual effects of acupuncture)
- unable to provide informed consent

## **7.0 RECRUITMENT PLAN**

All MM, HD, and NHL patients who are scheduled to receive auto-HSCT at the Adult Bone Marrow Transplantation (BMT) Service at a participating study site will be screened for eligibility by the clinical and/or research staff in the study. All such patients will be screened and enrolled, if eligible, regardless of their gender or ethnicity/race.

Potential research subjects will be identified by a member of the patient's treatment team, a protocol investigator, or research staff. If the investigator is a member of the treatment team, s/he will screen their patient's medical records for suitable research study participants and discuss the study and their potential for enrolling in the research study. Potential subjects contacted by their treating physician will be referred to the investigator/research staff of the study. The principal investigator and research staff may also screen the medical records of patients with whom they do not have a treatment relationship for the limited purpose of identifying patients who would be eligible to enroll in the study and to record appropriate contact information in order to approach these patients regarding the possibility of enrolling in the study.

During the initial conversation between the investigator/research staff and the patient, the patient may be asked to provide certain health information that is necessary to the recruitment and enrollment process. The investigator/research staff may also review portions of their medical records in order to further assess eligibility. They will use the information provided by the patient and/or medical record to confirm that the patient is

eligible and to contact the patient regarding study enrollment. If the patient turns out to be ineligible for the research study, the research staff will destroy all information collected on the patient during the initial conversation and medical records review, except for any information that must be maintained for screening log purposes.

In most cases, the initial contact with the prospective subject will be conducted either by the treatment team, investigator or the research staff working in consultation with the treatment team. The recruitment process outlined presents no more than minimal risk to the privacy of the patients who are screened and minimal PHI will be maintained as part of a screening log. For these reasons, MSK and participating sites seek a (partial) limited waiver of authorization for the purposes of (1) reviewing medical records to identify potential research subjects and obtain information relevant to the enrollment process; (2) conversing with patients regarding possible enrollment; (3) handling of PHI contained within those records and provided by the potential subjects; and (4) maintaining information in a screening log of patients approached (if applicable).

The research staff in conjunction with the clinical staff will explain to an eligible patient the study, potential risks and benefits of participating in the study, that participation in the research study is completely voluntary, and that they have the right to refuse participation or withdraw at any point in the study without influencing any aspect of their medical treatment. Once a patient is deemed eligible, they may be enrolled through an in-person consent appointment, econsent or by a verbal consent conducted over the phone. For patients interested in consenting remotely, they may be enrolled through MSK eConsent modules to conduct electronic consent as in Section 8.0. Patients who do not have a desktop or laptop computer capable of a remote econsent and who cannot travel to study sites may be consented using a verbal consent.

Similarly, at participating sites, each week, study staff will review new incoming BMT patients for eligibility. Staff will receive a list of new patients every week and will screen for eligibility using available electronic health records. If a patient is eligible based upon medical record review, a consent coordinator on the patient's medical team and/or the research coordinator will provide the patient with initial study information either virtually (via Zoom) or in person at the SCCA clinic. If the patient is interested and eligible, study staff will consent the participant and enroll them into the study prior to initiation of BMT treatment.

## 7.1 Research Participant Registration

Confirm eligibility as defined in the section entitled Inclusion/Exclusion Criteria. Obtain informed consent, by following procedures defined in section entitled Informed Consent Procedures. Written documentation of consent form and authorization will be waived for verbal consent. See Section 8.0 for Informed Consent procedures. During the registration process registering individuals will be required to complete a protocol specific Eligibility Checklist. The individual signing the Eligibility Checklist is confirming whether the participant is eligible to enroll in the study. Study staff are responsible for ensuring that all institutional

requirements necessary to enroll a participant to the study have been completed. See related Clinical Research Policy and Procedure #401 (Protocol Participant Registration).

## 7.2 Randomization

After registration, research staff will randomize patients via MSK's secure Clinical Research Database (CRDB) using permuted blocks of random length. The allocation ratio will be 1:1 for ACU:OPI. Using the institutional randomization standard procedure with random blocks for RCTs will ensure full allocation concealment. Randomization will be stratified by study site, primary cancer diagnosis (MM versus HD versus NHL) and transplantation setting (inpatient versus outpatient) to ensure these characteristics are comparably distributed between the two study arms.

## 8.0 INFORMED CONSENT PROCEDURES

### Scenario 1: Standard written consent scenario

The consent form/research authorization meets the requirements of the Code of Federal Regulations and the Institutional Review Board/Privacy Board of this Center. The consent form will include the following:

1. The nature, objectives, potential risks, and benefits of the intended study.
2. The length of study, what it entails, and the likely follow-up required.
3. Alternatives to the proposed study. (This will include available standard and investigational therapies. In addition, patients will be offered an option of supportive care for therapeutic studies.)
4. The name of the investigator(s) responsible for the protocol.
5. The right of the participant to accept or refuse study interventions/interactions and to withdraw from participation at any time.
6. How the participants' data will be protected, who will have access to their PHI, and what data will be disclosed for research purposes

Prior to inclusion in the study and before protocol-specified procedures are carried out, the consenting professionals will explain the details of the protocol as outlined in the consent and research authorization to the participants/LARs. The participant/LAR will also be informed that they are free to withdraw from the study at any time. The consent discussion may occur in person or remotely via teleconference, telephone, or videoconference.

All participants/LARs must sign an IRB/PB-approved consent form/research authorization indicating their consent to participate. Each participant/LAR and consenting professional will sign and date the consent form. The participant/LAR must receive a copy of the signed informed consent form.

**Scenario 2:** Documentation of consent waived (e.g., verbal consent, only consenting professional signs)

The verbal informed consent/research authorization meets the requirements of the Code of Federal Regulations and the Institutional Review Board/Privacy Board of this Center. The consent/research authorization script will include the following:

1. The nature, objectives, potential risks, and benefits of the intended study.
2. The length of study, what it entails, and the likely follow-up required.
3. Alternatives to the proposed study.
4. The name of the investigator(s) responsible for the protocol.
5. The right of the participant to accept or refuse study interventions/interactions and to withdraw from participation at any time.
6. How the participants' data will be protected, who will have access to their PHI, and what data will be disclosed for research purposes.

Prior to inclusion in the study and before protocol-specified procedures are carried out, consenting professionals will explain the details of the protocol to participants/LARs. Participants/LARs will also be informed that they are free to withdraw from the study at any time. The consent discussion may occur in person or remotely via teleconference, telephone, or videoconference.

The consenting professional must sign an IRB/PB-approved consent /research authorization script to document the consent discussion and the participant's agreement.

In following the Code of Federal Regulations Title 45, Part 46, Subpart A, the IRB is waiving the requirement for an investigator to obtain a signed consent form from the participant as the research:

- presents no more than minimal risk of harm to participants, and
- involves no procedures for which written consent is normally required outside of the research context.

In following the Code of Federal Regulations Title 45, Part 164, Subpart E, IRB/PB is waiving the requirement for the investigator to obtain signed research authorization from the participant as:

- the use or disclosure of the PHI involves no more than minimal risk to the privacy of the individuals, based on the following elements:

- o An adequate plan to protect identifiers from improper use and disclosure;
- o An adequate plan to destroy the identifiers at the earliest opportunity consistent with conduct of the research (unless there is a health or research justification for retaining the identifiers, or such retention is otherwise required by law); and
- o Adequate written assurances that the PHI will not be reused or re-disclosed to any other person or entity, except as required by law, for authorized oversight of the research project, or for other research for which the use of disclosure of PHI would be permitted by HIPAA.
  - The research could not be practicably conducted without access to and use of the PHI.
  - The research could not practicably be conducted without the waiver.

If a verbal consent is being conducted, the consenting professional will use the IRB/PB-approved verbal informed consent script when calling patients. If the patient agrees to participate, the consenting professional will sign and date the verbal consent, and a copy will be sent to the patient. A verbal consent would be used in cases where individuals do not have access to a computer and those who are unable to travel to study sites for an in-person consent appointment. This research involves no more than minimal risk to participants and use of a verbal consent would not adversely affect the rights and welfare of the research participants.

Informed consent can be obtained remotely with a telehealth platform and through an electronic-consenting process, using the MSK eConsent module. Electronic consent will be made available to potential patients who wish to enroll using the MSK eConsent modules. At participating sites, electronic consent will be made available to potential patients who wish to enroll using MSK's REDCap eConsent platform. FH/SCCA may use MSK's REDCap eConsent platform to electronically consent potential patients, and the MSK study team will maintain the REDCap eConsents. All participants/LARs must sign an IRB/PB-approved consent form via REDCap indicating their consent to participate. A consenting professional signature is not required as noted in IRB SOP IC-706. The participant/LAR must receive a copy of the signed informed consent form. Consenting professionals will perform the informed consent procedures using a telehealth audio/video platform. A copy of the written informed consent with standard research authorization document will be available as a file download for the patient's reference. Contact information for the study team will also be available should participants need to reach out with any questions. Patients interested in study participation will be able to sign the electronic consent once they have reviewed the consent form in its entirety and discussed the study with the consenting professional. Those who decline participation will not be contacted further. Reasons for refusal to take part in the study will be tracked if provided. Once consented, a PDF copy of the electronic consent form will be stored in the project's file repository survey archive. This document will record the date stamp, participant identifier information, IP address and the consent version number. A copy of the consent will be sent to the participant via email or standard mail based on his/her preference.

MSK may verbally consent patients, whereas FH/SCCA will always obtain written consent. The participant must receive a copy of the signed or verbal informed consent form, and a copy of the signed or verbal consent form will be sent to the patient's EMR.

## 9.0 PRE-TREATMENT/INTERVENTION

Enrolled patients will receive the following baseline assessments within 4 weeks before the first dose of HiChemo. Detailed descriptions of each assessment are in Section 11.0 and 13.1.

- Demographic and Clinical Features
- Symptom Burden (MDASI-BMT), paper or electronic
- Brief Pain Inventory – Short Form (BPI), paper or electronic
- Patient-Reported Oral Mucositis Symptom Scale (PROMS) ,paper or electronic
- Pain Medication Side Effects Questionnaire,paper or electronic
- Quality of Life (PROMIS-29), paper or electronic
- Adverse Events (CTCAE v5)
- Opioid Risk Tool (ORT), paper or electronic
- Acupuncture Expectancy Scale (AES), paper or electronic

## 10.0 TREATMENT/INTERVENTION PLAN

All study patients will receive the usual HSCT care and pain management regimens as per standard practice at the study institution. For patients randomized to the ACU group, they will receive acupuncture as follows.

In addition to usual care, patients in the ACU group will receive acupuncture treatments. Acupuncture treatments will be scheduled to cover the period of high symptom burden. Acupuncture will start on Day 0 and continue once daily to Day 15, as long as the patient is inpatient or comes to the clinic for post-transplantation follow-up. For myeloma patients getting melphalan, the day of melphalan infusion is counted as Day 0 in the study. For lymphoma patients getting BEAM (carmustine, etoposide, cytarabine, melphalan), the day of melphalan infusion is counted as Day 0. For lymphoma patients getting TBC (thiotepa, busulfan and cyclophosphamide), the day of thiotepa infusion is counted as Day 0. For the occasional patients on investigational conditioning chemotherapy regimen, Day 0 will be determined by the BMT physician and the PI.

Acupuncture will not be done on days patients are neutropenic (absolute neutrophil counts <500/microliter) or thrombocytopenic (platelet counts <20,000/microliter). Acupuncture does not have to be done on days when acupuncturists are not available, for example during weekend days or on days there is a staff shortage, or when a patient declines an

acupuncture treatment. The total number of acupuncture treatment a patient has received will be recorded. Patients will be instructed to do self-acupressure at LI-4 and PC-6 acupuncture points when they experience pain or nausea.

Patients in the OPI group will receive usual care and will not receive acupuncture.

In this study, acupuncture needles will be inserted at bilateral PC6, LI4, ST36, SP6, KI3, LR3, and ear shenmen acupuncture points and unilateral GV20 and Ex-HN3 points. The needles will be manually manipulated for deqi and left in place for 20 minutes before removal. Electrical stimulation (e-acupuncture) may be applied to the ST36 and SP6 points when appropriate as per standard acupuncture practice.

Prior to acupuncture, the acupuncturist will check the patient's Complete Blood Counts (CBC) from the same day (HSCT patients have daily CBCs and will not provide the treatment if the patient's absolute neutrophil counts are less than 500/microliter or platelet counts less than 20,000/microliter. If an acupuncture point falls on an area of skin that is not safe to do acupuncture (e.g. wound or skin infection), the point will not be used and the deviation from point prescription will be recorded. A needle counting will be performed at the end of the treatment to ensure all needles are removed. Any adverse event noted during or immediately after acupuncture will be addressed according to standards in the profession of acupuncture and documented in the research record. Any serious adverse event will be reported to the study PI or a co-I immediately.

Participants will be asked to complete patient reported outcomes assessments online using REDCap or, if they prefer, via pencil and paper or over the phone with a Clinical Research Coordinator to reduce participant burden and ensure timely completion.

## 11.0 EVALUATION DURING TREATMENT/INTERVENTION

We will assess all study participants for the study outcomes at baseline (within 4 weeks before HiChemo) and on or about days 7, 15, 30, and 90 after the first dose of HiChemo (See Schema in Section 4.0). The total burden in time to patients is about 30-45 minutes at each time point.

The following outcome measurements will be carried out on and about Day 7, 15, 30 and 90 (Day 0 being the day of first dose of HiChemo), either in the Integrative Medicine or BMT clinic in order to minimize unnecessary visits. The instruments are attached in appendices, and may be administered electronically (on a tablet if in clinic, via secure link if at home) or on paper.

- Opioid Use (drug administration record while inpatient and pill count while outpatient)
- Symptom Burden (MDASI-BMT)
- Brief Pain Inventory – Short Form (BPI)

- Patient-Reported Oral Mucositis Symptom Scale (PROMS)
- Pain Medication Side Effects Questionnaire
- Quality of Life (PROMIS-29)
- Adverse Events (CTCAE v5)

Collection of demographic and clinical features (diagnosis, disease status, chemotherapy regimen and mortality) data and assessment of use of healthcare resources will also be carried out on and about Day 90. Use of healthcare resources includes the length of hospital stays and transfers to the intensive care unit during HSCT, and total inpatient days, emergency room visits and readmissions during the first 30 days post-HSCT.

Schema of Data Collection	By Patient vs. By Study Team (ST)	Baseline	Day 7 (± 2 day)	Day 15 (± 3 days)	Day 30 (± 7 days)	Day 90 (± 14 days)
Demographic and Clinical Features	ST	X				X
Opioid Use (Primary Outcome)	Patient and ST	X	X	X	X	X
Symptom Burden (MDASI-BMT)	Patient	X	X	X	X	X
Brief Pain Inventory – Short Form (BPI)	Patient	X	X	X	X	X
Patient-Reported Oral Mucositis Symptom Scale (PROMS)	Patient	X	X	X	X	X
Pain Medication Side Effects Questionnaire	Patient	X	X	X	X	X
Quality of Life (PROMIS-29)	Patient	X	X	X	X	X
Adverse Events (CTCAE v5)	ST	X	X	X	X	X
Opioid Risk Tool (ORT)	Patient	X				
Acupuncture Expectancy Scale (AES)	Patient (ACU)	X				
Use of Health Care Resources	ST					X

\*Day 0 = Day of the first dose of high dose chemotherapy

## 12.0 CRITERIA FOR REMOVAL FROM STUDY

Patients will be considered off-study upon completion of Day 90 assessments. Study intervention will be discontinued if severe, unexpected adverse events attributable to acupuncture has occurred or discontinuation is deemed by the principal investigator to be in the best interest of the patient. Those patients will remain in the study for outcome assessments. Patients will be removed from the study if the patient wishes to withdraw from the study. Removed patients will continue to be evaluated for outcomes if they give permission for us to do so.

## 13.0 CRITERIA FOR OUTCOME ASSESSMENT AND ENDPOINT EVALUABILITY

### 13.1 Criteria for Therapeutic Response/Outcome Assessment

Demographic data (age, gender, race, ethnicity, height and weight) and clinical features (cancer diagnosis, disease status, and regimen of the high-dose chemotherapy) will be collected.

Our first primary outcome is the proportion of patients who are opioid users (the number of patients using opioids at a given time divided by the total number of patients randomized to that group at Day 7 and Day 90). In this study, we define opioid user as a patient who uses any opioids during the seven days preceding the day of assessment. At baseline, patients will be asked whether they have a prescription for any opioids, any access to non-prescription opioids and whether they used any opioids in the preceding seven days. During an inpatient period, all administrations of pain medications are recorded on hospital drug administration records, which will serve as our primary data source. For outpatient, we will use pill-counting to collect this data and data on opioid dose actually consumed by the patient in the week prior to the time point (Appendix 2). Pill-counting can be done remotely with a telehealth platform.

Our second primary outcome is the symptom burden at Day 7, measured by the MDASI-BMT Total Symptom Severity score. MDASI-BMT (M.D.Anderson Symptom Inventory – Blood and Marrow Transplantation) is a 24-item multi-symptom patient-reported outcome (PRO) measure for clinical and research use. The MDASI-BMT consists of the core MDASI plus 5 items specific to BMT patients. It assesses 13 core symptoms common across cancer types and treatments (pain, fatigue, nausea, disturbed sleep, distress, shortness of breath, difficulty remembering, lack of appetite, drowsiness, dry mouth, sadness, vomiting, and numbness/tingling). In addition to the 13 core symptom items, it has 6 items that assess symptom-related interference. The MDASI has several advantages over other symptom-assessment scales in that it applies broadly across cancer types and treatments, is easy for patients to complete, includes items related to symptom interference with daily life, and it is easily translated into other languages. It takes five minutes to complete and has a Cronbach alpha reliability range from 0.82 to 0.94. For MDASI-BMT, five additional symptoms important to this population were added. The BMT symptoms rated are feeling physically sick, weak, diarrhea, mouth sores, and bleeding. All symptoms are rated with reference to “the last 24 hours” on 0–10 numeric scales from “not present” to “as bad as you can imagine.” Patients also rate the amount of interference with daily activities caused by symptoms on 0–10 numeric scales from “did not interfere” to “interfered completely.” The MDASI-BMT has demonstrated good internal reliability in prior studies. Three symptom and one interference subscale scores can be calculated from the MDASI-BMT items by taking the means of particular item subsets: Core Symptom Severity (13 core MDASI items), BMT Symptom Severity (5 BMT-specific items), Total Symptom Severity (13 core plus 5 BMT-specific items), and Interference (6 interference items). The subscale scores may be calculated when more than half of the items on a subscale have valid, non-missing responses, and should otherwise be considered missing. In the current study, the MDASI-BMT Total Symptom Severity score will serve as the symptom burden primary endpoint.

The Brief Pain Inventory–Short Form (BPI, internal consistency Cronbach's  $\alpha$  of 0.77–0.91) is a well-validated and widely used instrument to assess pain in cancer patients. It uses numerical rating scales (NRS) to quantify pain intensity and patient interference. The BPI

contains 4 pain severity items and 7 pain interference items, all rated on a scale from 0 to 10 (higher ratings indicate worse pain intensity/interference). A pain interference subscale can be computed by taking the average rating of the 7 pain interference items. A pain severity subscale score can similarly be computed for the 4 pain severity items; however, the Worst Pain severity item and the Average Pain severity item are often examined separately from the pain intensity subscale in clinical research because they tend to be more sensitive indicators of changes in patients' perceived pain. As such, the primary outcome of this study will be the patient's rating of their Worst Pain in the past week with response choices of 0 "no pain" to 10 "pain as bad as you can imagine." The Average Pain rating in the past week and the pain interference subscale will be used as secondary pain outcomes. This takes 5 minutes to complete.

Because the main source of pain in the study population is mucositis caused by high-dose chemotherapy, we will complement the BPI with an instrument that specifically assesses mucositis pain. We will use the PROMS (Patient-Reported Oral Mucositis Symptom) scale, which was developed using HSCT patients from baseline to 60 days post-HSCT (similar to our study population), has excellent psychometric properties, and is easy to administer. The PROMS scale has ten items, each quantified through a 100-mm Visual Analog Scale (VAS), and a Cronbach's  $\alpha$  of 0.86–0.98. This takes 3 minutes to complete.

Side effects are a major concern for patients using opioids. There is currently no gold standard instrument for specifically evaluating opioid side effects. We will use the method from Martel et al., which is specific for opioids side effects. Patients will be asked to complete a questionnaire in which they rate the intensity of each of the following symptoms in the last 24 hours on a visual analog scale (VAS) that ranges from 0 (minimum) to 10 (maximum): 1) nausea, 2) constipation, 3) headaches, 4) dry mouth, 5) itching, 6) sneezing, 7) sweating, 8) weakness, 9) dizziness, 10) confusion, 11) memory problems, and 12) visual problems. This takes 2 minutes to complete.

We will assess patients' overall quality of life (QOL) using the Patient-Reported Outcomes Measurement Information System 29 Items (PROMIS-29), which resulted from a National Institutes of Health initiative to develop state-of-the-science self-report measures to assess functioning and well-being in physical, mental and social domains of health. The PROMIS-29 v2.0 profile measure is analogous to the most widely used profile measure to date, the SF-36. But the PROMIS-29 v2.0 profile items were selected from PROMIS item banks calibrated using item response theory (IRT) analyses and all items in a domain are scored on the same underlying metric. This takes 10 minutes to complete.

We will monitor and record adverse events (AEs) as per the Common Terminology Criteria for Adverse Events Version 5.0 (CTC-AE v5.0). The adverse events will be collected by the study team, and assessed (grade/attribution) by the clinician. The Opioid Risk Tool (ORT) is a brief, self-report screening tool designed for use with adult patients to assess risk for opioid abuse. It is recommended by the National Institute on Drug Abuse (NIDA) as an instrument

to screen for opioid misuse risk, and takes 2 minutes to complete. This data will be collected at baseline and used in Heterogeneity of Treatment Effect (HTE) analysis to assess whether it influences the effects of acupuncture. Expectancy for acupuncture may influence its clinical effects. We will assess patients at baseline using the Acupuncture Expectancy Scale (AES). This is a validated instrument (takes about 3 minutes to complete) with an internal consistency (Cronbach's  $\alpha$ ) of 0.95 and test-retest reliability of 0.62 over four weeks without acupuncture treatment. This data will be used as a variable in HTE analyses for predictor to response and sensitivity analyses. We will also track use of healthcare resources, such as the length of hospital stays and transfers to the intensive care unit during HSCT, and emergency room visits and readmission during the first 30 days post-HSCT. These are exploratory endpoints to generate preliminary data about impact on the health care system, e.g. iatrogenic adverse events from opioids and delayed discharge from opioid side effects.

All patient-reported measures will be administered either electronically (on a tablet if in clinic, via secure link if at home) or on paper.

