### **6.1 Participant Inclusion Criteria**

- age 18 or older
- pathological diagnosis of MM, HD or NHL
- scheduled for high dose chemotherapy for auto-HSCT in the following month (30 days)
- not taking opioids regularly in the week prior to consent (one-time dosing of opioids for a painful procedure is allowed)

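### The seven-day look-back for the Day 7 opioid endpoint moves with the visit date, so patients seen on Days 5 to 9 are scored on different days and the endpoint is misclassified

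*Combined protocol and SAP*

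**What the plan says.** Section 13.1 sets the rule for the first primary outcome: "we define opioid user as a patient who uses any opioids during the seven days preceding the day of assessment". The schedule table in Section 11.0 gives the Day 7 assessment a window of two days either side and the Day 90 assessment a window of 14 days either side.

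For inpatients, Section 13.1 states that "all administrations of pain medications are recorded on hospital drug administration records, which will serve as our primary data source". For outpatients it uses pill counts to obtain "data on opioid dose actually consumed by the patient in the week prior to the time point", and refers to Appendix 2, which Section 18.0 lists but whose text is not available. That wording can be read as the nominal day, so Section 13.1 contains two possible anchors.

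Day 0 is also defined in two ways. Section 11.0 has "Day 0 being the day of first dose of HiChemo". Section 10.0 has "For lymphoma patients getting BEAM (carmustine, etoposide, cytarabine, melphalan), the day of melphalan infusion is counted as Day 0". Acupuncture is tied to Day 0: "Acupuncture will start on Day 0 and continue once daily to Day 15".

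The primary model in Section 14.2.2 contains arm and stratification variables, with no term for the actual assessment day. Sections 13.2 and 14.4 require only that opioid use was assessed. Neither gives a rule for early or late visits.

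**The concern.** A seven-day look-back measured from a visit that may fall anywhere in a five-day window does not cover the same days for every patient. Section 3.0 says mucositis pain starts shortly after HiChemo and peaks around Day 7, so opioid use is probably changing quickly over exactly these days.

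At the early end, the look-back reaches days before acupuncture could have acted. Because any single opioid dose makes a patient a user, one dose on Day -2 or -1 is enough. Eligibility does not exclude this. The criterion is "not taking opioids regularly in the week prior to consent (one-time dosing of opioids for a painful procedure is allowed", and patients need only be "scheduled for high dose chemotherapy for auto-HSCT in the following month (30 days", so the opioid-free week can end up to 30 days before treatment.

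This endpoint carries alpha of 0.02 (Section 14.1). At stake are the sharpness of the Day 7 contrast and, if visit timing happened to differ by arm, its error rate.

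**Working it through.** **1. The plan's own power figure.** Section 14.1 gives 81% power for 25% versus 10% users with 135 evaluable per arm at two-sided alpha 0.02, and expects similar power at Day 7. The normal approximation has null SE √(2 × 0.175 × 0.825/135) = 0.0462 and alternative SE √((0.25 × 0.75 + 0.10 × 0.90)/135) = 0.0453. Power is Φ((0.15 − 2.326 × 0.0462)/0.0453) = 82.5%. A Wald test on the log odds ratio gives 79.4%. The stated 81% lies between them and is not in question.

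**2. Days covered.** A visit on Day v covers Days v−7 to v−1.

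| Visit | Look-back | Days before Day 0 |
|---|---|---|
| Day 5 | −2 to 4 | 2 |
| Day 6 | −1 to 5 | 1 |
| Day 7 | 0 to 6 | 0 |
| Day 8 | 1 to 7 | 0 |
| Day 9 | 2 to 8 | 0 |

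Day 5 and Day 9 visits share Days 2 to 4 only. A Day 5 visit misses Days 5 and 6. For Day 90 the look-back ranges from Days 69–75 to Days 97–103. It moves too, but contains no day before treatment.

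**3. Dilution, equal in both arms.** Suppose pre-Day-0 doses turn a fraction c of non-users into users, so that p becomes p + (1 − p)c. The values of c are assumed, because the documents give none.

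| c | ACU | OPI | Power |
|---|---|---|---|
| 0 | 10.0% | 25.0% | 82.5% |
| 2% | 11.8% | 26.5% | 77.5% |
| 5% | 14.5% | 28.75% | 70.0% |
| 10% | 19.0% | 32.5% | 58.4% |

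These are upper bounds, because they treat every patient as seen early. If one patient in four were seen on Days 5 or 6 and 5% of their non-users were affected, c = 0.25 × 5% = 1.25% and power is 79.4%.

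**4. Error rate if timing differed by arm.** This needs two assumed inputs: a slope in the proportion of users per day of later assessment, and a gap in mean assessment day between arms. With no treatment effect, the spurious difference is d = slope × gap. The rejection rate is Φ((d − 2.326 × SE₀)/SE₁) + Φ((−d − 2.326 × SE₀)/SE₁), with proportions 25% ± d/2, 140 per arm and SE₀ = √(2 × 0.25 × 0.75/140) = 0.0518.

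| Gap | d at 3 to 5 points per day | Two-sided error (nominal 2%) |
|---|---|---|
| ¼ day | 0.75 to 1.25 | 2.1% to 2.4% |
| ½ day | 1.5 to 2.5 | 2.5% to 3.5% |
| 1 day | 3 to 5 | 4.2% to 8.7% |

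With 135 per arm the one-day figures are 4.1% to 8.4%.

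As a check on the slope, assume constant daily onset, use that persists once started, and 25% users by Day 6. If onset begins on Day 0, the daily hazard is 1 − 0.75^(1/7) = 0.040. If it begins on Day 3, it is 1 − 0.75^(1/4) = 0.069. Moving from a Day 6 to a Day 7 visit then adds 3.1 points (21.9% to 25.0%) or 5.6 points (19.4% to 25.0%). The pilot figures in Section 3.0 (sham arm 20% at Day 5, 40% around Day 30) average (40 − 20)/25 = 0.8 points per day, but say nothing about the slope near Day 7.

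**The case against.** A reader might infer that the moving window biases the trial in favour of acupuncture, because only that arm has planned daily treatment to Day 15 and the trial has no sham control. The documents do not support this.

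- No section says visit timing will differ by arm. A one-day mean gap is large inside a window of two days either side: half of one arm would have to be seen two days off while the other arm was on time.
- Sections 10.0 and 16.0 describe daily blood counts for transplant patients generally, so both arms have frequent contact. Questionnaires can be completed from home (Section 11.0) and pill counts done remotely (Section 13.1).
- Doses before Day 0 should be balanced by randomization. They weaken the contrast and do not favour an arm.

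A reader might also say that early visits count doses given before any chemotherapy. Under the Section 10.0 definition that need not hold for BEAM patients. What can be said is that those days precede the start of acupuncture.

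Finally, the outpatient window may already be fixed. The phrase about the week before the time point may mean the nominal day, and Appendix 2 may settle it. This stands as far as it goes: for outpatients the defect is an unresolved ambiguity. It does not reach the inpatient definition, for which Section 13.1 gives no other anchor.

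**Conclusion.** The point holds as a measurement problem. As written, the Day 7 user definition covers days that depend on the visit date, and nothing in the evaluability criteria, analysis populations or primary model corrects for it. Whenever visits fall off Day 7, the effect is misclassification and dilution. Its size cannot be taken from the documents, because they give neither the spread of visit days nor the frequency of opioid use on Days -2 and -1.

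Directional bias is conditional on a difference in visit timing between arms. The error rates above illustrate what such a difference would do under an assumed slope. They are not a forecast. The look-back before Day 0 concerns the Day 7 endpoint only, and the planned sample size and power calculation are not in error. The change is worth making because it is nearly free and concerns a primary endpoint.

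**What to change.** - **Inpatient days:** score Day 7 opioid use from the dated drug administration records over fixed Days 0 to 6, whatever the visit date.
- **Outpatients:** keep a seven-day look-back, and state in Section 13.1 and Appendix 2 whether it is anchored on the actual assessment day or the nominal day. Do not replace it with a pill count running from Day 0 to the visit: that would cover 5 days (0 to 4) for a Day 5 visit and 9 days (0 to 8) for a Day 9 visit, so user status would still depend on visit date.
- **All patients:** record the actual assessment day and add a sensitivity analysis adjusting for it. Assessment day arises after randomization, so this should support the primary model and not replace it.
- **Day 0:** reconcile Sections 10.0 and 11.0, so that Days 0 to 6 mean the same thing for every regimen.

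The cost is protocol and SAP wording, one recorded date and one extra analysis. No new inpatient data are needed, and the planned sample size is unchanged. The downside is that outpatient timing stays less exact than inpatient timing. Randomization is stratified by transplantation setting (Section 7.2), so that difference should be roughly balanced between arms.
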